- a. Patients randomized to receive the oral immunonutrition supplementation in addition to standard of care will complete a daily compliance log documenting their intake of the provided supplements.
- b. All patients will complete a weekly survey rating their pain score (VAS) and any symptoms/side effects experienced during their study participation.
- c. At the final visit, subjects randomized to receive the oral immunonutrition supplementation will complete a satisfaction survey in which they detail their thoughts on their treatment plan.

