### **Appendix 3: Biweekly Clinic Survey (Weeks 2, 4, 6)**

## **Effects of Supplemental Immunonutrition on Healing of Chronic Non-Healing Lower Extremity Ulcers in Diabetic Patients: Clinic Survey**

Name: \_\_\_\_\_ Date: \_\_\_\_\_

1. Which follow-up visit are you being seen for today?  
 2-week visit  
 4-week visit  
 6-week visit
2. Did you receive immunonutrition supplements (Omega-3 fatty acids, Vitamin C, L-Arginine)?  
 Yes (proceed to question 3) \_\_\_\_\_  
 No (proceed to question 4)
3. Have you experienced any difficulty taking the supplementation according to the instructions?  
 Yes, please explain: \_\_\_\_\_  
 No
4. Have you experienced any of the following symptoms since your surgery? Check all that apply:  

 Abdominal Pain	 Low Blood Pressure
 Heartburn	 Burping
 Nausea	 Taste Perversion
 Vomiting	 Constipation
 Diarrhea	 Gastrointestinal Disorder
 Headache	 Itchy Skin
 Insomnia	 Easy bleeding or bruising
 Rash	 Red, itchy welts
 Indigestion	 Other, please explain: _____
 Palpitations	_____
 Numbness	
 Bitter Taste	
5. Have you made any trips to Emergency Departments/Urgent Care Centers since your last visit related to your foot ulcer?  
 Yes, please explain: \_\_\_\_\_  
 No
6. Circle your current level of pain related to your foot ulcer on the scale below:

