#### **If the subject is enrolled in the treatment arm (received oral immunonutrition supplementation), proceed with questions 3 and 4. If not, skip to question 5:**

- 3) **Verification of supplementation:** "Did you receive supplementation and instructions on how it should be taken?"
  1. **If No:** "May I ask why not?"
  2. **If Yes:** *proceed to number 3*
- 4) **Medication compliance:** "Have you been able to take the supplementation daily as instructed?"
  1. **If No:** "May I ask why not?"
  2. **If Yes:** *proceed to number 3*
- 5) **Experienced symptoms:**
  1. "Have you experienced any of the following symptoms during your participation in the study. Please answer yes or no to each"
    - Abdominal pain, heartburn, nausea, vomiting, diarrhea, headache, insomnia, rash, indigestion, palpitations, numbness, bitter taste, low blood pressure, burping, taste perversion, constipation, gastrointestinal disorder, itchy skin, easy bleeding or bruising, red itchy welts
    - "Have you experienced any other symptoms"
      - If yes:** "can you please explain?"
      - If no:** *proceed to number 5*
- 6) **Emergency Department / Urgent Care Visits:** "Since beginning this study, have you had any unscheduled office visits, or have you been to any emergency departments or urgent care centers related to your foot ulcer?"
  1. **If Yes:** "Can you please explain?"
  2. **If No:** *proceed to number 6*

"Thank you for your time (*Patient name*), I hope you have a good day."

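### The clinic symptom question (Appendix 3, Q4) has no negative answer, so a blank cannot be told from no symptoms, while the phone survey asks the same list with a yes or no to each

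*Combined protocol and SAP*

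**What the plan says.** Specific Aim 2 (section 2) rests tolerability on a survey of both arms: "All patients will complete a weekly survey rating their pain score (VAS) and any symptoms/side effects experienced during their study participation". Two instruments deliver it.

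- **Clinic survey, weeks 2, 4 and 6 (Appendix 3).** Question 4 reads "Have you experienced any of the following symptoms since your surgery? Check all that apply". Twenty symptoms and an 'Other' line follow the instruction "Check all that apply". There is no 'None' box and no yes/no per symptom. Questions 3 and 5 on the same form each offer a 'No'.
- **Phone survey, weeks 1, 3 and 5 (Appendix 4).** Question 5 covers the same 20 symptoms over the patient's participation in the study, with the instruction "Please answer yes or no to each". It then asks about any other symptoms.

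The Procedures section (6f) cites these two appendices the other way round; this note follows the appendices' own titles. Neither the Statistical Analysis section (6h) nor the Data Management section (6i) says how an unmarked question 4 is to be coded.

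The surveys are not the only source of adverse events. The Safety Monitoring Plan (section 9) also names office visits and chart review, and section 6f schedules an interval history and physical examination at weeks 2, 4 and 6.

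**The concern.** An unmarked question 4 has at least three readings: the patient had no symptoms, skipped the question, or overlooked an item. The stem adds a fourth. It refers to a surgery, although the study defines none, so a patient who has had no operation may take the question as not applicable.

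No coding rule can repair this afterwards. If blanks are read as 'no', skipped questions become symptom-free patients. If blanks are read as missing, every truly symptom-free patient drops out, and all remaining forms show at least one symptom.

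Supplementation side effects are listed as a key data point in section 6i, and section 7 states that the risks of this combination are unknown. The Data Safety Committee reviews recorded adverse events after every five enrolments. With 15 patients per arm, a few lost answers are a visible share of the data. A change in recorded symptoms between odd and even weeks could also reflect the form and not the patient.

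**Working it through.** The plan states no symptom rate or completion rate, so there is no figure of its own to reproduce. The check compares the two forms and then gives a scale under stated assumptions.

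**1. The forms side by side**

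| | Clinic (Appendix 3, Q4) | Phone (Appendix 4, Q5) |
|---|---|---|
| Weeks | 2, 4, 6 | 1, 3, 5 |
| Symptoms listed | 20 plus 'Other' | the same 20 plus any other |
| Negative answer | none | yes or no to each |
| Period in the wording | since surgery | participation in the study |
| Arms | both, same wording | both, same wording |

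**2. Forms affected**

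The plan has 30 patients, 15 per arm (section 6c), and three clinic surveys each: 30 x 3 = 90 forms, 15 x 3 = 45 per arm, if all attend. This is three of the six scheduled symptom contacts.

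**3. What later calls recover**

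Phone question 5 looks back over participation. A symptom left unmarked at week 2 is asked about again, with an explicit answer, at week 3, and one left unmarked at week 4 is asked about again at week 5. No such call follows week 6. The later safety contact is for the treatment group only and concerns events after the supplement was stopped. For symptoms first arising after the week 5 call, the week 6 clinic form is therefore the only checklist in both arms: 30 forms, 15 per arm.

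**4. Scale for a single clinic contact (assumed inputs)**

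Let p be the true any-symptom rate and s the share of forms on which question 4 is skipped. Assume that skipping is unrelated to symptoms, that blanks are read as 'no', and that nothing is recovered elsewhere. Then the recorded rate is p(1 - s), and the expected loss is 15ps patients per arm.

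| p | s = 5% | s = 10% | s = 20% |
|---|---|---|---|
| 20% | 19% (0.15 lost) | 18% (0.30) | 16% (0.60) |
| 40% | 38% (0.30) | 36% (0.60) | 32% (1.20) |
| 60% | 57% (0.45) | 54% (0.90) | 48% (1.80) |

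For example, 0.40 x (1 - 0.10) = 0.36, and 15 x 0.40 x 0.10 = 0.60.

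**5. Is it differential by arm?**

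With the same s in both arms, the recorded difference is (pT - pC)(1 - s), where pT and pC are the true rates in the treated and control arms. A true difference shrinks by the fraction s, and a true difference of zero stays zero. Nothing in the documents suggests that s differs by arm.

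**The case against.** The strongest reply is that other sources cover the gap. A provider takes a history and examines the patient at the same visits at which the clinic form is used, charts are reviewed throughout, and the week 3 and week 5 calls ask again about earlier symptoms. This largely stands. It limits the consequence for any-symptom-during-study mainly to the last week, and the table above overstates the loss wherever a call or history recovers the answer. It does not make the clinic form interpretable, and it leaves no second checklist after week 5.

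It is also fair to say that symptom rate is not a named endpoint in section 6e and is not among the modelled outcomes in section 6h. The data serve Specific Aim 2 and safety review, which keeps the point modest.

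A reader might go further in three ways that the documents do not support.

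- *Skipped answers are counted as symptom-free.* No coding rule is given. The supported statement is that blank and 'none' cannot be told apart, and understated rates follow only if blanks are coded 'no'.
- *Side effects are elicited differently by arm.* Within each form, the wording, list and answer format are identical for both arms. Only the lead-in differs. On the clinic form, controls also answer question 2, which names the supplements, and skip only question 3 ("Have you experienced any difficulty taking the supplementation according to the instructions"). On the phone, treated patients "proceed with questions 3 and 4. If not, skip to question 5" applies to the rest. This could produce an order effect, but its size is unknown. No placebo is described, so patients know their arm in any case.
- *The checklist is the only controlled tolerability data.* It is the only structured symptom list put to both arms, but adverse events are recorded by other routes as well.

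**Conclusion.** The point holds as a defect of one form. Clinic question 4 cannot separate no symptoms from no answer, in either arm, and it does not match the format that the sponsor already uses by phone for the same 20 symptoms. Up to 90 forms carry the ambiguity. The part with no later checklist is the 30 week 6 forms, for symptoms arising after the week 5 call, and history, examination and chart review may still capture those.

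The size of any loss cannot be derived from the documents. The range of 16% to 57% recorded for true rates of 20% to 60% rests wholly on assumed skip shares of 5% to 20%, on blanks being read as 'no', and on no recovery elsewhere. The ambiguity is not in itself differential by arm. The conclusion does not depend on any effect of question order. The change is worth making because it is nearly free, not because a large bias has been shown.

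**What to change.** - In Appendix 3, question 4, replace the tick-list with a yes/no answer for each of the 20 symptoms, as in Appendix 4.
- At minimum, add a 'None of these' box. This identifies a wholly skipped question, but an overlooked single item still cannot be told from a denied one.
- State in section 6h or 6i that an unanswered item is missing, not 'no', and report the number missing by arm and week.
- In the same edit, align the stem of question 4 with the since-enrolment period in the schedule of events.

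The cost is one revised form and a slightly longer paper survey, with no extra visits, staff or patients.

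Moving the supplement questions (clinic Q3; phone Q3 and Q4) after the symptom list is optional and not needed for this point. It would remove one arm-specific cue, but any priming could then move to the answers on compliance and difficulty, which bear on the tertiary outcome.

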  - a. If randomized to the control group (SOC only), patients will receive standard of care defined as sharps debridement, appropriate dressing, and offloading. If randomized to the treatment group (SOC + Immunonutrition), subjects will receive standard of care defined as sharps debridement, appropriate dressing, and offloading in addition to a 6-week supply of Omega-3 fatty acids (soft gel form, 2 pills per day, total of 1.68 grams) and L-Arginine/Vitamin C (powder form, to be mixed with 8 oz liquid, 1 scoop once daily, total of 4.5 grams L-arginine and 500 mg vitamin C). Subjects will also be provided a compliance log with detailed instructions for taking and tracking supplements.
5. Patients will be scheduled for biweekly wound checks with their provider (weeks 2, 4, 6). Wound characteristics will be documented at each follow up visit using the PUSH Tool 3.0, images of the wound will be obtained, and an interval history and physical exam will be documented. The provider will verify and document concomitant medications in the patient's chart. The provider will visualize and evaluate any additional wounds that are present (new or present at time of enrollment) and record characteristics in the patient's chart. Patients will complete a questionnaire detailing their pain level (VAS), symptoms experienced during the treatment phase, and any unscheduled visits to emergency departments/urgent care centers. This will be completed via a paper survey in clinic during their office visit (Appendix 4). On weeks where an office visit is not scheduled (weeks 1, 3, 5), a research coordinator will call the patient and collect survey responses (Appendix 3).
6. At the final office visit (week 6), plantar pressure profiles will be recorded via the Tekscan Pressure Mat, and clinical plantar weight-bearing images will be captured. Patients randomized to receive the oral immunonutrition supplementation will complete an additional survey detailing their satisfaction with the treatment plan and any additional thoughts they would like to share (Appendix 5) and return the completed compliance log

(Appendix 6). Patients in the treatment arm will have CMP and lipid panel labs drawn at this timepoint or within 3 months of study completion.

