7. A follow-up safety visit will be conducted by the provider for patients randomized to the treatment group 6-8 weeks after the week 6 office visit. This visit is more than 5 half-lives after supplementation discontinuation and will allow for capture of adverse events that may occur after completion of dosing. The wound will be visualized during this visit. Adverse events and wound details will be documented in the patient's chart. This visit will be conducted in-office if the patient is already scheduled to see their provider within the visit window. If the patient is not scheduled to see their provider, this visit may be conducted virtually through EPIC.
8. Patient charts will be monitored throughout the patient's participation in the study for any signs of infection, unscheduled visits, calls to the provider, and/or onset of severe adverse events. Patient charts will continue to be monitored for one year following the completion of the study to assess ulcer recurrence rates.

The schedule of events is outlined below and is pictured in Appendix 1:

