**Continuous Patient Monitoring:**

Patients enrolled in this study will be flagged in EPIC as a participant in a research study. If a patient presents to an Emergency Department and/or is admitted to a Prisma Health hospital, the study team will be notified via EPIC. The patient's chart will be reviewed to determine the cause of the admission and promptly reported to the study investigators.

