**Adverse Event (AE) and Serious Adverse Event (SAE) Reporting:**

Adverse events will be recorded at in-office visits, via study coordinator phone calls, and through manual chart review. All AEs will be reported to the wound care provider, if they are not already aware of the event. Serious adverse events will be immediately reported to all study investigators.

Patients who experience an adverse event (AE) assessed as  $\geq$  Grade 3 (and  $\geq$  Grade 2 for bone marrow and cardiovascular events) per NCI-CTCAE version 5.0^19 will discontinue use of the oral supplement, if in the treatment arm. These subjects will continue to be monitored until the AE resolves or stabilizes. AEs and SAEs will be promptly reported to the IRB and FDA, as required.

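### Both surveys limit the emergency and urgent-care question to foot-ulcer visits, although Procedures step 5 sets no such limit, so visits for other reasons can be missed

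*Combined protocol and SAP*

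**What the plan says.** Section 6.f, step 5 describes the questionnaire that patients complete at each contact. Besides pain and symptoms, it is to detail "any unscheduled visits to emergency departments/urgent care centers". No cause is specified.

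Two forms put this into practice:

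- Appendix 3 question 5, the clinic form for weeks 2, 4 and 6: "Have you made any trips to Emergency Departments/Urgent Care Centers since your last visit related to your foot ulcer"?
- Appendix 4 question 6, the phone form for weeks 1, 3 and 5: "have you had any unscheduled office visits, or have you been to any emergency departments or urgent care centers related to your foot ulcer"?

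Other routes could also pick up an unscheduled visit. Section 9, under Continuous Patient Monitoring, sets up an electronic alert: "If a patient presents to an Emergency Department and/or is admitted to a Prisma Health hospital, the study team will be notified via EPIC". Section 6.f, step 8 has charts monitored for "any signs of infection, unscheduled visits, calls to the provider, and/or onset of severe adverse events". Section 9, under adverse event reporting, adds: "Adverse events will be recorded at in-office visits, via study coordinator phone calls, and through manual chart review". The office visits at weeks 2, 4 and 6 include an interval history, an examination and a check of concomitant medication. Both forms carry a symptom checklist with an open item for anything else.

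**The concern.** A form is the working version of the protocol: staff ask what is printed on it. Here both printed questions are narrower than the instruction they implement, and the part left out matters for safety. A visit tied to the ulcer mostly signals a wound complication. A visit for palpitations, low blood pressure, bleeding or vomiting, all listed in Section 7 as possible supplement effects, is the kind that might signal harm from the intervention. A patient who made such a visit could truthfully answer no to both questions.

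Section 7 states that the three supplements have not been studied together in people and that the risks of the combination are unknown. Section 9 requires adverse events to be graded, makes continuation of the supplement depend on the grade, requires immediate reporting of serious events to the investigators, and has the Data Safety Committee review recorded events after every 5 patients enrolled. All of this depends on knowing not only that a symptom occurred but how bad it was and whether it led to urgent care.

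**Working it through.** The plan gives no figure on this point and the check needs no calculation. It compares the instruction with each route by which a non-ulcer emergency or urgent-care visit could come to light.

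| Source | Covers non-ulcer emergency or urgent-care visits? | Limit |
|---|---|---|
| Section 6.f, step 5 (the instruction) | Yes, any cause | None stated |
| Appendix 3 question 5 | No | Ulcer-related only |
| Appendix 4 question 6 | No | Ulcer-related only; also asks about unscheduled office visits, where the reach of the restriction is unclear |
| Symptom checklist (Appendix 3 question 4, Appendix 4 question 5) | Not directly | Records the symptom, with no field for severity or for where care was sought |
| Interval history at weeks 2, 4, 6 | Possibly | No question on outside visits is specified; not part of the phone contacts |
| Electronic alert (Section 9) | Yes, where it fires | The only hospitals named belong to the home system |
| Chart monitoring (Section 6.f, step 8; Section 9) | Yes, if charted | The visit has to reach the chart |

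**Step 1: is it a matter of timing?** No. The clinic question looks back to the last visit and the phone question to the start of the study, so together they span the six weeks. The gap comes from the restriction on cause.

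**Step 2: how many contacts carry the restricted wording?** Three clinic contacts plus three phone contacts make six per patient. With the planned 30 patients that is 6 × 30 = 180 scheduled contacts. This counts times the narrower question is asked. It does not count lost visits.

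**Step 3: follow one visit through.** Suppose a patient in the supplement arm goes to an emergency department with palpitations. The visit question is answered no. The checklist gets a tick for palpitations. Unless the alert fires, the record reaches the chart, or the patient mentions the visit, the study holds a symptom with no severity and no sign that emergency care was needed. The symptom is captured; its seriousness or grade may not be.

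**Step 4: how firm is the checklist as a fallback?** The phone version asks about symptoms during study participation. The clinic version asks about symptoms since a surgery, although enrolment involves none. That weakens the clinic checklist somewhat but does not remove it.

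**The case against.** The strongest reply is that the plan has several safety nets and the visit question is only one. That is largely right. Bleeding, low blood pressure, palpitations, vomiting and rash are all on the symptom lists of both forms, with an open item as well, and both arms answer them at every contact. The interval history and medication check may bring out a visit. Chart monitoring for unscheduled visits carries no ulcer restriction. Treated patients also have a safety follow-up 6 to 8 weeks after week 6, and the supplement arm's charts are reviewed daily, though that review is described in connection with surgery planning.

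A reader might therefore be tempted by three stronger readings that the documents do not support:

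- That serious supplement-related events go unrecorded. The symptoms are asked about directly. What can be lost is the visit, and with it the evidence on seriousness or grade.
- That visits outside the home system are invisible. The alert sentence is ambiguous: the system's name may qualify only the hospital admission and not the emergency department. The documents do not say whether outside records reach EPIC. Limited reach is a reasonable inference, not a stated fact.
- That a definite share of visits would be missed. The documents give neither a rate of non-ulcer visits nor the proportion made elsewhere, so no expected number follows.

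What survives the reply is narrower. None of these routes is a structured question about non-ulcer emergency or urgent-care visits, and step 5 promises one.

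**Conclusion.** The concern holds as a contradiction between the protocol text and its own forms. Used as printed, both surveys collect less safety information than step 5 requires, at every scheduled contact and in both arms. Non-ulcer emergency and urgent-care visits can be missed, above all where a facility's records may not reach EPIC. That last part rests on the inference about the alert's reach; the mismatch in wording does not.

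The number of visits affected cannot be estimated. For scale only: with 15 patients in the supplement arm, one patient whose serious event was not recognised as such would be 1/15 = 6.7% of those exposed. That shows how much a single event weighs in a pilot of this size and says nothing about how likely it is.

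The primary endpoint, the sample size and the planned analysis are not affected. The forms should be corrected because the change is small and the plan itself describes the risks of the combination as unknown.

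**What to change.** 1. In Appendix 3 question 5 and Appendix 4 question 6, delete the closing restriction to the ulcer (the words from 'related' onwards), so that both match step 5.
2. Ask the reason for each visit. Both forms already prompt for an explanation after a yes, so that space can hold it.
3. Add a Yes/No field for whether the visit was related to the foot ulcer. This keeps the ulcer-specific count.
4. In the same revision, correct the reference to surgery in Appendix 3 question 4, and the appendix numbers in step 5, which assign the clinic and phone surveys the opposite way round from the appendix titles.

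The cost is a wording change on two forms, one extra field, and slightly more visit reasons to code. No treatment, visit schedule or clinical rule changes.
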